6.6.1 Stopping Rules

The following stopping rules will be used during the conduct of this study.

If any of the below stopping rules are met, the study will be paused, and no further dosing will occur until the Sponsor has reviewed the totality of data available. To continue the study (on joint agreement with the Sponsor and investigator), an amendment will be submitted for approval.

1. An individual participant reports an SAE considered related to the study intervention by the investigator.
2. Two (2) or more participants within a Panel (at the same dose level) report Severe Nonserious AEs considered related to the study intervention by the investigator.

If any of the below stopping rules are met, subsequent higher doses in Part 1 will be lowered based on joint agreement of the Sponsor and investigator in order for the study to continue.

3. Should the emerging PK (mean) data indicate that the maximum clinical exposure (C_{\max} or AUC), as defined in Section 4.3.2 will be exceeded, subsequent higher doses will be adjusted based on joint agreement of the Sponsor and investigator.

4. CCI [REDACTED]
5. CCI [REDACTED]
6. CCI [REDACTED]

6.7 Intervention After the End of the Study

There is no study-specified intervention after the end of the study.

6.8 Clinical Supplies Disclosure

This study is blinded, but in Part 1 supplies are provided open label; therefore, an unblinded pharmacist or qualified study-site personnel will be used to blind supplies. Study intervention identity (name, strength, or potency) is included in the label text; random code/disclosure envelopes or lists are not provided.

The emergency unblinding call center will use the intervention randomization schedule for the study to unblind participants and to unmask study intervention identity. The emergency unblinding call center should only be used in cases of emergency (see Section 8.1.10). The Sponsor will not provide random code/disclosure envelopes or lists with the clinical supplies.

6.9 Standard Policies

Not applicable

7 DISCONTINUATION OF STUDY INTERVENTION AND PARTICIPANT WITHDRAWAL

7.1 Discontinuation of Study Intervention

Discontinuation of study intervention does not represent withdrawal from the study. As certain data on clinical events beyond study intervention discontinuation may be important to the study, they must be collected through the participant's last scheduled follow-up, even if the participant has discontinued study intervention. Therefore, all participants who discontinue study intervention before completion of the protocol-specified treatment period will still continue to participate in the study as specified in Section 1.3 and Section 8.1.9, or if available, a PCL.

Participants may discontinue study intervention at any time for any reason or be discontinued from the study intervention at the discretion of the investigator should any untoward effect occur. In addition, a participant may be discontinued from study intervention by the investigator or the Sponsor if study intervention is inappropriate, the study plan is violated, or for administrative and/or other safety reasons. Specific details regarding procedures to be performed at study intervention discontinuation are provided in Section 8.1.9.

A participant must be discontinued from study intervention, but continue to be monitored in the study, for any of the following reasons:

The participant or participant's legally acceptable representative requests to discontinue study intervention.

The participant's treatment assignment has been unblinded by the investigator, MSD subsidiary, or through the emergency unblinding call center.

The participant has a medical condition or personal circumstance which, in the opinion of the investigator and/or Sponsor, placed the participant at unnecessary risk from continued administration of study intervention.

The participant has a confirmed positive serum pregnancy test.

The participant has a positive drug screen at any time during the course of the study. The drug screen can be confirmed by a recheck at the discretion of the investigator after discussion with the Sponsor.

The participant meets any of the individual stopping rules described in Section 7.1.1.

Discontinuation from study intervention is "permanent." Once a participant is discontinued from study intervention, they shall not be allowed to restart study intervention.

7.1.1 Individual Stopping Criteria

CCI [Redacted]

[Redacted]

- I [Redacted]
- I [Redacted]
- I [Redacted]
- I [Redacted]
- I [Redacted]

[Redacted]

[Redacted]

[Redacted]

[Redacted]

[Redacted]

- I [Redacted]
- I [Redacted]

CCI

7.2 Participant Withdrawal From the Study

A participant must be withdrawn from the study if the participant or participant's legally acceptable representative withdraws consent from the study.

If a participant withdraws from the study, they will no longer receive study intervention or be followed at scheduled protocol visits.

Specific details regarding procedures to be performed at the time of withdrawal from the study, as well as specific details regarding withdrawal from FBR, are outlined in Section 8.1.9. The procedures to be performed should a participant repeatedly fail to return for scheduled visits and/or if the study site is unable to contact the participant are outlined in Section 7.3.

7.3 Lost to Follow-up

If a participant fails to return to the clinic for a required study visit and/or if the site is unable to contact the participant, the following procedures are to be performed:

The site must attempt to contact the participant and reschedule the missed visit. If the participant is contacted, the participant should be counseled on the importance of maintaining the protocol-specified visit schedule.

The investigator or designee must make every effort to regain contact with the participant at each missed visit (eg, telephone calls and/or a certified letter to the participant's last known mailing address or locally equivalent methods). These contact attempts should be documented in the participant's medical record.

8 STUDY ASSESSMENTS AND PROCEDURES

Study procedures and their timing are summarized in the SoA.

Adherence to the study design requirements, including those specified in the SoA, is essential and required for study conduct.

The investigator is responsible for ensuring that procedures are conducted by appropriately qualified (by education, training, and experience) staff. Delegation of study-site personnel responsibilities will be documented in the Investigator Trial File Binder (or equivalent).

All study-related medical decisions must be made by an investigator who is a qualified physician.

All screening evaluations must be completed and reviewed to confirm that potential participants meet all eligibility criteria. The investigator will maintain a screening log to record details of all participants screened and to confirm eligibility or record reasons for screening failure, as applicable.

Procedures conducted as part of the participant's routine clinical management (eg, blood count) and obtained before providing documented informed consent may be used for screening or baseline purposes provided the procedures meet the protocol-specified criteria and were performed within the time frame defined in the SoA.

Additional evaluations/testing may be deemed necessary by the investigator and or the Sponsor for reasons related to participant safety. In some cases, such evaluation/testing may be potentially sensitive in nature (eg, HIV, hepatitis C), and thus local regulations may require that additional informed consent be obtained from the participant. In these cases, such evaluations/testing will be performed in accordance with those regulations.

Procedures conducted as part of a site generic screening (with an ERC/IRB approved site generic screening consent) on potential participants (eg, blood count, vital signs, ECG, etc) and obtained before signing of study ICF may be used for screening or baseline purposes provided the procedures met the protocol specified criteria and were performed within the screening window defined in this protocol.

The maximum amount of blood collected from each participant over the duration of the study will not exceed the volume mentioned in Appendix 8.

Repeat or unscheduled samples may be taken for safety reasons or for technical issues with the samples.

8.1 Administrative and General Procedures

8.1.1 Informed Consent

Informed consent will adhere to IRB/IEC requirements, applicable laws and regulations, and Sponsor requirements. The ICF, any subsequent revised ICF, and any written information

provided to the participant must receive the IRB/IEC's approval/favorable opinion in advance of use.

Informed consent given by the participant (or their legally acceptable representative) must be documented on a consent form. The form must include the study protocol number, study protocol title, dated signature, and agreement of the participant (or their legally acceptable representative) and of the person conducting the consent discussion.

A copy of the signed and dated ICF should be given to the participant (or their legally acceptable representative) before participation in the study.

The investigator or medically qualified designee (consistent with local requirements) must obtain documented informed consent from each potential participant (or their legally acceptable representative) prior to participating in this clinical study or FBR. If there are changes to the participant's status during the study (eg, health or age of majority requirements), the investigator or medically qualified designee must ensure the appropriate documented informed consent is in place.

8.1.1.1 General Informed Consent

Specifics about the study and the study population are to be included in the ICF.

The participant (or their legally acceptable representative) should be informed in a timely manner if new information becomes available that may be relevant to the participant's willingness to continue participation in the study. The communication of this information will be provided and documented via a revised consent form or addendum to the original consent form that captures the participant's or the participant's legally acceptable representative's dated signature.

8.1.1.2 Consent and Collection of Specimens for Future Biomedical Research

The investigator or medically qualified designee will explain the FBR consent to the participant, or the participant's legally acceptable representative, answer all of his/her questions, and obtain documented informed consent before performing any procedure related to FBR. A copy of the informed consent will be given to the participant before performing any procedure related to FBR.

8.1.2 Inclusion/Exclusion Criteria

All inclusion and exclusion criteria will be reviewed by the investigator, who is a qualified physician, to ensure that the participant qualifies for the study.

8.1.3 Participant Identification Card

All participants will be given a participant identification card identifying them as participants in a research study. The card will contain study-site contact information (including direct telephone numbers) to be used in the event of an emergency. The investigator or qualified designee will provide the participant with a participant identification card immediately after

the participant provides documented informed consent. At the time of intervention randomization, site personnel will add the treatment/randomization number to the participant identification card.

The participant identification card also contains contact information for the emergency unblinding call center so that a health care provider can obtain information about study intervention in emergency situations where the investigator is not available.

8.1.4 Medical History

[figure not shown]
A medical history will be obtained by the investigator or qualified designee.

8.1.5 Prior and Concomitant Medications Review

[figure not shown]
8.1.5.1 Prior Medications

The investigator or qualified designee will review before medication use, including any protocol-specified washout requirement, and record prior medication taken by the participant within 2 months before starting the study.

cc

CCI

8.1.5.2 Concomitant Medications

The investigator or qualified designee will record medication, if any, taken by the participant during the study.

8.1.6 Assignment of Screening Number

All consented participants will be given a unique screening number that will be used to identify the participant for all procedures that occur before randomization. Each participant will be assigned only 1 screening number. Screening numbers must not be reused for different participants.

Any participant who is screened multiple times will retain the original screening number assigned at the Screening Visit. Specific details on the screening/rescreening visit requirements are in Section 8.11.1. Pre-trial screening logs may be collected for review by the Sponsor. If applicable, any information that would make the participant identifiable will be removed.

8.1.7 Assignment of Randomization Number

All eligible participants will be randomly allocated and will receive a randomization number. The randomization number identifies the participant for all procedures occurring after randomization. Once a randomization number is assigned to a participant, it can never be reassigned to another participant.

A single participant cannot be assigned more than 1 randomization number.

8.1.8 Study Intervention Administration

Part 1

Study intervention will be administered by the investigator and/or an appropriately qualified designee at the site.

Part 2

Participants will be instructed on how to administer at home study intervention by the site staff.

While participants are at the site, the study medication will be taken by the participant under supervision from the site staff. Following study administration, the participant will complete the Study Medication Diary followed by site staff verification that the diary has been completed properly.

In each treatment period, on Day 2 before being discharged from the site, participants will receive their assigned bottle of study intervention for unsupervised administration at home for Day 2 afternoon dose and for Days 3 to 6. Upon participants return to the site on Day 6, the study intervention bottle will be collected by the site staff in preparation for Day 7 treatment administration at the site.

8.1.8.1 Timing of Dose Administration

CCI

[REDACTED]

[REDACTED]

[REDACTED]

[REDACTED]

[REDACTED]

[REDACTED]

8.1.9 Discontinuation and Withdrawal

The investigator or study coordinator must notify the Sponsor when a participant has been discontinued/withdrawn from the study and/or intervention. If a participant discontinues for any reason at any time during the course of the study and/or intervention, the participant may be asked to return to the clinic (or be contacted) for a poststudy visit as per the number of days described in Section 8.11.4. to have the applicable procedures conducted. However, the investigator may decide to perform the poststudy procedures at the time of discontinuation or

as soon as possible after discontinuation. If the poststudy visit occurs prior to the safety follow-up time frame as specified in Section 8.4.1, the investigator should perform a follow-up telephone call at the end of the follow-up period (Section 8.4.1) to confirm if any AEs have occurred since the poststudy clinic visit. Any AEs that are present at the time of discontinuation/withdrawal should be followed in accordance with the safety requirements outlined in Section 8.4.

8.1.9.1 Withdrawal From Future Biomedical Research

Participants may withdraw their consent for FBR. Participants may withdraw consent at any time by contacting the study investigator. If medical records for the study are still available, the investigator will contact the Sponsor using the designated mailbox ([contact]). Subsequently, the participant's consent for FBR will be withdrawn. A letter will be sent from the Sponsor to the investigator confirming the withdrawal. It is the responsibility of the investigator to inform the participant of completion of withdrawal. Any analyses in progress at the time of request for withdrawal or already performed before the request being received by the Sponsor will continue to be used as part of the overall research study data and results. No new analyses would be generated after the request is received.

If the medical records for the study are no longer available (eg, if the investigator is no longer required by regulatory authorities to retain the study records) or the specimens have been completely anonymized, there will no longer be a link between the participant's personal information and their specimens. In this situation, the request for specimen withdrawal cannot be processed.

8.1.10 Participant Blinding/Unblinding

STUDY INTERVENTION IDENTIFICATION INFORMATION IS TO BE UNMASKED ONLY IF NECESSARY FOR THE WELFARE OF THE PARTICIPANT. EVERY EFFORT SHOULD BE MADE NOT TO UNBLIND.

For emergency situations where the investigator or medically qualified designee (consistent with local requirements) needs to identify the intervention used by a participant and/or the dosage administered, he/she will contact the emergency unblinding call center by telephone and make a request for emergency unblinding. As requested by the investigator or medically qualified designee, the emergency unblinding call center will provide the information to him/her promptly and report unblinding to the Sponsor. Before contacting the emergency unblinding call center to request unblinding of a participant's intervention assignment, the investigator who is qualified physician should make reasonable attempts to enter the intensity of the AEs observed, the relation to study intervention, the reason thereof, etc, in the medical record. If it is not possible to record this assessment in the medical record before the unblinding, the unblinding should not be delayed.

If unblinding has occurred, the circumstances around the unblinding (eg, date, reason, and person performing the unblinding) must be documented promptly, and the Sponsor Clinical Director notified as soon as possible.

Once an emergency unblinding has taken place, the investigator, site personnel, and Sponsor personnel may be unblinded so that the appropriate follow-up medical care can be provided to the participant.

Participants whose treatment assignment has been unblinded by the investigator or medically qualified designee and/or nonstudy treating physician must be discontinued from study intervention, but should continue to be monitored in the study.

8.1.11 Domiciling

CCI

[REDACTED]

[REDACTED]

[REDACTED]

[REDACTED]

8.1.12 Calibration of Equipment

The investigator or qualified designee has the responsibility to ensure that any device or instrument used for a clinical evaluation/test during a clinical study that provides information about inclusion/exclusion criteria and/or safety or efficacy parameters shall be suitably calibrated and/or maintained to ensure that the data obtained are reliable and/or reproducible. Documentation of equipment calibration must be retained as source documentation at the study site.

8.2 Efficacy/Immunogenicity Assessments

There are no direct efficacy assessments in this study.

8.3 Safety Assessments

Details regarding specific safety procedures/assessments to be performed in this study are provided below. The total amount of blood to be drawn over the course of the study (from prestudy to poststudy visits), including approximate blood volumes drawn by visit and by sample type per participant, can be found in the Central Laboratory Services Manual.

Planned time points for all safety assessments are provided in the SoA.

8.3.1 Physical Examinations

A complete physical examination will be conducted by an investigator or medically qualified designee (consistent with local requirements) per institutional standard. Height and weight will also be measured and recorded.

Investigators should pay special attention to clinical signs related to previous serious illnesses.

8.3.2 Neurological Examinations

General and targeted neurological examinations will be conducted according to the procedures outlined in Appendix 10.

8.3.3 BMI

BMI equals a person's weight in kilograms divided by height in meters squared ($\text{BMI} = \text{kg/m}^2$). BMI will be rounded to the nearest whole number according to the standard convention of 0.1 to 0.4 round down and 0.5 to 0.9 round up.

Body weights and height will be obtained with the participant's shoes off and jacket or coat removed.

8.3.4 Vital Signs

Body temperature, PR, RR, and BP will be assessed. **The same method must be used for all measurements for each individual participant and should be the same for all participants at a given site.**

Resting and orthostatic BP and HR will be assessed with a completely automated device. Manual techniques will be used only if an automated device is not available. Resting BP and HR position can be seated or semi-recumbent. The same position must be used for all measurements for each individual participant and should be the same for all participants at a given site.

VS will be measured after at least 10 minutes rest for the participant in a quiet setting without distractions and will include temperature, systolic and diastolic BP, HR and RR.

8.3.4.1 Resting Vital Signs

Vital Sign Measurements (Heart Rate and Blood Pressure)

Participants should be resting in a quiet setting without distractions for at least 10 minutes before having VS measurements obtained. VS will include HR, systolic and diastolic BP, RR, and body temperature at timepoints indicated in the SoA. The correct size of the BP cuff and the correct positioning on the participant's arm is essential to increase the accuracy of BP measurements.

At screening, HR and BP will be in triplicate measurements, obtained at least 1 minute apart (all 3 sets completed within 6 minutes). The median of the three measurements will be used to assess for participants eligibility.

Part 1

In each treatment period, the predose (baseline) HR and BP will be in triplicate measurements, obtained at least 1 minute apart (all 3 sets completed within 6 minutes) within 3 hours of dosing MK-6552. The median of these measurements will be used as the baseline to calculate change from baseline for safety evaluations (and for rechecks, if needed). Postdose VS measurements will also be measured in triplicate measurements.

Part 2

In each treatment period, on Days 1 and 7, the predose (baseline) HR and BP will be in triplicate measurements, obtained at least 1 minute apart (all 3 sets completed within 6 minutes) within 3 hours of dosing MK-6552/placebo. The median of these measurements will be used as the baseline to calculate change from baseline for safety evaluations (and for rechecks, if needed). All postdose VS measurements will be single measurements.

Poststudy visit HR and BP will be in triplicate measurements, obtained at least 1 minute apart (all 3 sets completed within 6 minutes).

Participants will continue to rest from dosing until 1 hour postdose except to stand for the measurement of orthostatic VS (if needed) or other study-related procedure.

Body Temperature

Body temperature will be measured in Part 1 only. The same method must be used for all measurements for each individual participant and should be the same for all participants at a given site.

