8.3.5 Electrocardiograms

All 12-lead ECGs will be obtained and reviewed by an investigator or medically qualified designee (consistent with local requirements) as outlined in the SoA using an ECG machine that automatically calculates the HR and measures PR, QRS, QT, and QTc intervals. Refer to Appendix 8 for evaluation and potentially significant findings.

At each time point when triplicate ECG are required, 3 individual ECG tracings should be obtained at least 1 minute apart. The full set of triplicates should be completed in no more than 6 minutes.

Special care must be taken for proper lead placement by qualified personnel. Skin should be clean and dry before lead placement. Participants may need to be shaved to ensure proper lead placement. Participants may need to remove interfering garments.

Participants should be resting for at least 10 minutes before each ECG measurement. The resting position may include seated, semi-recumbent or supine, but the same position must be used for all measurements for each individual participant and should be the same for all participants at a given site.

The correction formula to be used for QTc is Fridericia.

If repeat ECGs are required, the clinical site will decide whether to leave the electrodes in place or mark the position of the electrodes for subsequent ECGs. To mark the position of the electrodes, 12-lead electrode sites will be marked on the skin of each participant with an ECG skin-marker pen to ensure reproducible electrode placement.

For all participants, screening and poststudy ECG recordings are to be obtained in single measurements.

Part 1

Before each treatment period, predose ECGs will be obtained in triplicate at least 1 minute apart within 3 hours before dosing MK-6552. The median of these measurements will be used as the baseline to calculate change from baseline for safety evaluations (and for rechecks, if needed).

In all treatment periods, postdose ECG will be in triplicate measurements at the time-points specified in the SoA.

Part 2

Before each treatment period, on Days 1 and 7, predose ECGs will be obtained in triplicate at least 1 minute apart within 3 hours before dosing MK-6552. The median of these measurements will be used as the baseline to calculate change from baseline for safety evaluations (and for rechecks, if needed).

All postdose ECG will be obtained as single measurements at the time-points specified in the SoA.

For both study parts

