During each treatment period, if a participant demonstrates a median increase in QTc interval ≥ 60 msec, or $\geq 25\%$ compared to the median predose baseline measurement, the participant will continue to be monitored by triplicate repeat ECGs every 30 minutes for at least 2 hours or until the abnormality is resolved. If prolongation of the QTc interval ≥ 60 msec persists over 120 minutes, a consultation with a cardiologist may be appropriate and the Sponsor should be notified (see Section 7.1.1).

During each treatment period, if the median QTc interval is ≥ 500 msec for postdose measurements and sustained for 120 minutes (see Section 7.1.1), the Sponsor should be notified, and the ECGs should be reviewed by a cardiologist. The participant should be telemetry monitored (until the QTc interval is < 500 msec) or should be considered for transfer to a location where closer monitoring and definitive care (eg, a CCU or ICU) is available.

If the median increase in QTc interval ≥ 60 msec, or $\geq 25\%$ compared to the median predose baseline measurement or median QTc interval is ≥ 500 msec for postdose measurements and these changes are sustained for 120 mins, the QTc individual stopping rule will be met and dosing to the particular participant should be halted and the Sponsor's clinical director informed within 24 hours:

If at any time the QRS interval is prolonged ≥ 200 msec (and change is not considered rate related or pacing induced), then the Sponsor should be notified. The ECGs should be reviewed by a cardiologist and the participant should be considered for transfer to a location where closer monitoring and definitive care (eg, a CCU or ICU) is available.

If the participant has unstable hemodynamics, or has any clinically significant dysrhythmias noted, the participant should be immediately transferred to an acute care setting for definitive therapy.

If prolongation of the QTc interval is noted, concomitant medications that prolong QTc interval should be held until the QTc interval is within 60 msec of baseline and the QTc interval is < 500 msec.

A cardiologist will be consulted by the investigator as needed to review ECG tracings with significant abnormalities.

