10.8 Appendix 8: 12-Lead Electrocardiogram Evaluation Criteria

	Screen Failure Criteria	Potentially Significant Postrandomization Findings
RHYTHM		
Sinus Tachycardia	>110 bpm	HR >110 bpm and HR increase of ≥ 25 bpm from baseline
Sinus Bradycardia	<40 bpm	HR <40 bpm and HR decrease of ≥ 5 bpm from baseline
Sinus Pause/Arrest	>2.0 seconds	>2.0 seconds
Atrial Premature Complex	>1 beat	≥ 3 beats
Ventricular Premature Complex	All	≥ 3 beats
Ectopic Atrial Rhythm	All	All
Junctional Rhythm	Junctional Rhythm with HR <40 bpm	Junctional Rhythm with HR <40 bpm
Idioventricular Rhythm	All	All
Atrial Fibrillation	All	All
Atrial Flutter	All	All
Supraventricular Tachycardia	All	All
Ventricular Tachycardia	All	All
AXIS		
Left Axis Deviation	RBBB With LAHB	New Onset LAHB
Right Axis Deviation	RBBB With LPHB	New Onset LPHB
CONDUCTION		
1st Degree AV Block	PR ≥ 230 ms	PR ≥ 230 ms + Increase of >15 ms; or PR Increase of >25%
2nd Degree AV Block	Mobitz Type II	Mobitz Type II
3rd Degree AV Block	All	All
LBBB	All	All
RBBB	RBBB With LAHB/LPHB as Defined Above	New Onset RBBB (Not Including Rate-related)
ICRBBB (QRS <120 ms)	No Exclusion	Nothing
Short PR/Preexcitation Syndrome	Delta Wave + PR <120 ms	Delta Wave + PR <120 ms
Other Intraventricular Conduction Delay	QRS ≥ 130 ms	QRS ≥ 130 ms + Increase of ≥ 10 ms
QTc (B or F)		
Male/Female	QTc ≥ 450 ms	QTc ≥ 500 ms or Increase of ≥ 60 ms From Baseline
HYPERTROPHY		
Atrial Abnormalities	Definite Evidence of P Mitrale or P Pulmonale	Definite Evidence of P. Mitrale or P. Pulmonale
Ventricular Abnormalities	Voltage Criteria for LVH Plus Strain Pattern	Voltage Criteria for LVH Plus Strain Pattern
MYOCARDIAL INFARCTION		
Acute or Recent	All	All
Old	All	All

	Screen Failure Criteria	Potentially Significant Postrandomization Findings
ST/T MORPHOLOGY		
ST Elevation Suggestive of Myocardial Injury	In 2 or more contiguous leads	In 2 or more contiguous leads
ST Depression Suggestive of Myocardial Ischemia	In 2 or more contiguous leads	In 2 or more contiguous leads
T-wave Inversions Suggestive of Myocardial Ischemia	In 2 or more contiguous leads	In 2 or more contiguous leads
Nonspecific ST-T Changes (In 2 or More Leads)	No exclusion	In 2 or more contiguous leads
PACEMAKER	All	All

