AV=atrioventricular; bpm=beats per minute; HR=heart rate; ICRBBB=incomplete right bundle branch block; LAHB=left anterior hemiblock; LPHB=left posterior hemiblock; LVH=left ventricular hypertrophy; mm=millimeter; ms=milliseconds; QTcB=QT correction using Bazett's formula; QTcF=QT correction using Fredericia formula; RBBB=right bundle branch block; ST/T=ST-segment/T wave. Baseline is defined as Predose Day 1.		

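### Part 2 labels the Day 7 predose value a safety baseline after six days of dosing, so Day 7 change scores can lose any carried-over shift; for ECGs this also conflicts with Appendix 8

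*Combined protocol and SAP*

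**What the plan says.** Section 8.3.4.1, Part 2, on resting vital signs: "In each treatment period, on Days 1 and 7, the predose (baseline) HR and BP will be in triplicate measurements". Section 8.3.5, Part 2: "Before each treatment period, on Days 1 and 7, predose ECGs will be obtained in triplicate at least 1 minute apart". Both continue with the same rule, in the ECG section "The median of these measurements will be used as the baseline to calculate change from baseline for safety evaluations".

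Section 8.1.8 has participants dosed at the site and then at home through Day 6, returning that day for site dosing on Day 7.

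The table in Appendix 8 (section 10.8), to which section 8.3.5 sends the reader for potentially significant findings, carries the note "Baseline is defined as Predose Day 1". Its QTc flag after randomization is "QTc ≥ 500 ms or Increase of ≥ 60 ms From Baseline". The QTc monitoring and halt rule in section 8.3.5 measures the increase "compared to the median predose baseline measurement", without naming a day.

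Section 9.3.1 counts ECGs and vital signs among the primary safety endpoints. Section 9.5.1 plans summaries of raw values and of change from baseline, counts of absolute QTc (up to 450, above 450, above 480, above 500 msec) and counts of QTc change (below 30, at least 30, at least 60 msec). Its visible text names no baseline day.

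**The concern.** Part 2 carries the multiple-day safety objective, which is primary. A value taken on Day 7 before that morning's dose, after six days of treatment, describes the participant on drug. If it is the reference for Day 7, the Day 7 change measures only the further rise after that day's dose. It leaves out whatever has built up or persisted since Day 1. Day 1 and Day 7 changes would then answer different questions under one label.

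For ECGs there is a second problem. Section 8.3.5 and Appendix 8 point to different reference days for the same Day 7 tracing, and the halt rule does not settle which applies.

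**Working it through.** The plan states no figure on this point, so there is nothing to reproduce. The check sets the passages side by side and applies one identity.

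**Passages**

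| Measure | Part 2 baseline in section 8.3 | Appendix 8 |
|---|---|---|
| BP, vital-sign HR | Predose Day 1 and predose Day 7 (8.3.4.1) | Not covered |
| ECG (rate, PR, QRS, QTc) | Predose Day 1 and predose Day 7 (8.3.5) | Predose Day 1 |
| QTc increase rule in 8.3.5 | Predose baseline, day not named | Predose Day 1 for the 60 ms flag |

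**Identity.** Let S be the Day 7 predose value minus the Day 1 predose value in the same period, and A the further rise after the Day 7 dose.

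- Day 7 change from Day 7 predose = A
- Day 7 change from Day 1 predose = S + A
- Difference = S exactly

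The placebo period does not restore S to the change scores. With subscripts for active and placebo, the placebo-adjusted Day 7 change is A_a − A_p on the Day 7 reference and (S_a + A_a) − (S_p + A_p) on the Day 1 reference. They differ by S_a − S_p.

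**QTc illustration.** All values are assumed, because the documents give none. Day 1 predose QTc is 410 ms.

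| S (ms) | A (ms) | From Day 7 predose | From Day 1 predose | 60 ms met? (Day 7 / Day 1 reference) | Absolute QTc |
|---|---|---|---|---|---|
| 0 | 45 | 45 | 45 | no / no | 455 |
| 5 | 55 | 55 | 60 | no / yes | 470 |
| 10 | 45 | 45 | 55 | no / no | 465 |
| 20 | 45 | 45 | 65 | no / yes | 475 |
| 30 | 30 | 30 | 60 | no / yes | 470 |

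The absolute value in each row is the same on either reference. The 25% limb of the rule is not reached in any row (0.25 × 410 = 102.5 ms).

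**How much could remain at Day 7 predose?** Assume two doses 6 h apart, so 24 − 6 = 18 h since the last Day 6 dose, and an effect that decays with half-life h. The share left is 0.5^(18/h).

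| h (assumed) | Share left |
|---|---|
| 2 h | 0.2% |
| 4 h | 4% |
| 6 h | 12.5% |
| 9.6 h | 27% |
| 24 h | 59% |
| constant effect | 100% |

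The 9.6 h row is 48/5. It is the longest half-life for which the minimum gap of 2 days between Part 2 periods, described in section 8.11.2 as a full washout, spans five half-lives. The five-half-life convention is an assumption here.

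**The case against.** A predose reference on each dosing day is a legitimate choice: it estimates the postdose response on that day. For BP nothing in the documents contradicts it, because Appendix 8 is a 12-lead ECG table with no BP criterion, and its heart-rate entries are ECG rhythm criteria. That stands. For BP and vital-sign HR the point is only that the reference is on treatment.

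The text also never says that Day 7 replaces Day 1. The wording about the median leaves open which day governs which change. One baseline per day is the natural reading, but it remains a reading. Parts of section 9.5.1, the individual stopping criteria in 7.1.1 and the day headings of the schedules are redacted, so a governing definition there cannot be excluded. That stands too, though the visible ECG passages would still disagree.

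If the effect follows exposure and the washout statement is right, S may be small: 27% or less of the effect for half-lives up to 9.6 h under the assumptions above. This is fair, but an effect can outlast plasma exposure, and the visible text does not show that S is negligible.

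Finally, a reader might infer that any sustained BP, HR or QTc effect disappears from the trial's results. The documents do not support that. Section 9.5.1 also summarises raw values and counts absolute QTc categories, the 500 ms criterion needs no baseline, Day 1 changes are unaffected, and raw Day 7 values can be compared with the placebo period. The Day 1 to Day 7 predose shift can be computed from data already collected.

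**Conclusion.** The point holds for Day 7 change scores in Part 2. On the day-specific reading they understate a rise from the period's pre-dose starting point by exactly S, for BP, HR and ECG measures. The counts of QTc change of at least 30 and at least 60 msec inherit the same loss, provided those counts are produced for Part 2; the only Part 1 restriction visible in that paragraph of 9.5.1 follows the sentence on means and confidence intervals.

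The size of S cannot be given. The half-life is redacted, and every value of S and A used above is an illustration. With S = 0 the two references agree.

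Separately, and for ECG measures only, section 8.3.5 and Appendix 8 give different reference days, and the increase rule names none. A tracing with S = 20 and A = 45 ms is a 45 ms increase on one reading and 65 ms on the other. This inconsistency does not depend on the size of S, although its practical effect does. Extending it to blood pressure would go beyond what Appendix 8 covers.

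Because a primary safety objective is involved and the remedy uses existing data, the wording should be settled before analysis.

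**What to change.** In section 9.5.1, name the baseline day for each Part 2 change-from-baseline summary. Report Day 7 predose and postdose changes in BP, HR and ECG measures, and the QTc change categories, from the median of the same period's Day 1 predose triplicate. Change from Day 7 predose can stay as an additional summary, labelled as a within-day response.

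The sponsor must reconcile the Part 2 baseline in 8.3.5, the QTc increase rule in the same section and the baseline note in Appendix 8, so that one stated reference applies to the ECG alert and stopping criteria. Which reference that should be is a clinical decision, and none is proposed here.

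The cost is wording and a little extra tabulation. Both triplicates are already collected, so no measurement or visit is added.
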